8.1 Disposition of Safety Population

The number of subjects in each of the following categories will be summarized by investigator for each treatment arm and overall.

- Subjects enrolled in this study;
- Subjects who took at least one dose of study drug;
- Subjects who completed all study drugs;
- Subjects who completed all DAAs (including those who discontinued RBV)
- Subjects who prematurely discontinued all study drugs;
- Subjects who completed the study;
- Subjects who prematurely discontinued from the study;

The number and percentage of subjects who discontinued all study drugs will be summarized by reason (all reasons) and by primary reason (per eCRF) for each treatment arm and overall. Similar summaries will be provided for discontinuations from the study.

The number and percentage of subjects will be calculated for:

- Subjects with interruption of all DAAs;
- Subjects with interruption of any DAA;
- Subjects with interruption of ABT-493/ABT-530;
- Subjects with interruption of SOF;
- Subjects with RBV dose modification.

DAA interruptions and RBV dose modifications will be summarized by treatment arm and overall. Reasons for study drug interruptions and RBV dose modifications will be presented in the CSR listings.

9.0 Study Drug Duration and Compliance

Study drug duration and compliance will be summarized on the ITT population by treatment arm and overall.

9.1 Study Drug Duration

Study drug duration is defined for each subject as the last study drug dose date minus the first study drug dose date plus 1 day.

Descriptive statistics (mean, standard deviation, median, minimum, and maximum) will be presented for study drug duration.

Study drug duration will be summarized with frequencies and percentages using the following categories:

- 1 to 15 days
- 16 to 30 days
- 31 to 45 days
- 46 to 60 days
- 61 to 75 days
- 76 to 90 days
- 91 to 105 days
- > 105 days

In addition, the number and percentage of subjects with study drug duration of ≥ 77 days for the 12-week arm or study drug duration ≥ 103 days for the 16-week arm will be summarized.

9.2 Compliance

For each kit (ABT-493/ABT-530, SOF, and RBV), the total number of tablets dispensed and returned is recorded for each of the three components of the study drug (ABT-493/ABT-530, SOF, and RBV). The compliance of a subject for each component

of the study drug during the Treatment Period will be calculated as the percentage of tablets taken relative to the total expected to be taken, which will be derived according to the duration of that subject's Treatment Period (date of last dose of study drug – date of first dose of study drug + 1). For ABT-493/ABT-530 and SOF, study drug interruptions recorded on the eCRF will not be subtracted from the treatment duration of that study drug. For RBV compliance, RBV dose modifications and interruptions (modification to 0 mg) as recorded on the RBV Dose Modifications eCRF will be used to modify the total number of RBV tablets expected to be taken. If a subject is not able to return any of the dispensed kit, that subject's compliance will be regarded as missing.

A subject is considered to be compliant for a component of the study drug (ABT-493/ABT-530, SOF, or RBV) if the percentage is between 80% and 120%. Compliance will be calculated for each subject and each component and will be summarized with the mean, median, standard deviation, minimum, and maximum by treatment arm and overall. A listing of compliance for each subject on each component will also be provided. The percentage of compliant subjects for each component will be summarized by treatment arm and overall, based on data as observed. Subjects with missing values for compliance will not be included in the denominator.

10.0 Efficacy Analysis

10.1 General Considerations

General Considerations

All efficacy analyses will be performed on the ITT population by treatment arm and overall, unless otherwise specified. To support the primary analysis, sensitivity analyses will also be conducted using the mITT-VF population.

Missing data will be imputed as described in Section 6.3 for analyses of the HCV RNA endpoints of SVR and virologic failure.

Plasma HCV RNA levels will be determined for each sample collected by the central laboratory using the Roche COBAS® AmpliPrep/COBAS® TaqMan® HCV Quantitative Test, v2.0. The lower limit of detection (LLOD) and lower limit of quantification (LLOQ) for this assay (regardless of genotype) are both 15 IU/mL.

HCV RNA results that are detectable but not quantifiable are reported as "< 15 IU/ML HCV RNA DETECTED" and those that are undetectable are reported as "HCV RNA NOT DETECTED" in the database.

The notation "HCV RNA < LLOQ" is used to represent all HCV RNA values < 15 IU/mL, including values reported as "HCV RNA NOT DETECTED" or "< 15 IU/ML HCV RNA DETECTED." HCV RNA \geq LLOQ are all quantifiable values of 15 IU/mL or greater.

Definitions for Efficacy Endpoints

A confirmed quantifiable value during treatment is defined as any two consecutive HCV RNA measurements \geq LLOQ (or 100 IU/mL for **Breakthrough**), either both during treatment or at the final treatment measurement and the next consecutive post-treatment measurement. A confirmed quantifiable post-treatment value is defined as any two consecutive post-treatment HCV RNA measurements \geq LLOQ.

Breakthrough = confirmed HCV RNA \geq 100 IU/mL after HCV RNA < LLOQ during the Treatment Period; or confirmed increase from nadir in HCV RNA (two consecutive HCV RNA measurements > 1 log₁₀ IU/mL above nadir) at any time point during the Treatment Period. A single breakthrough value (\geq 100 IU/mL or > 1 log₁₀ above nadir) followed by lost to follow-up also will be considered a breakthrough (i.e., will not require confirmation).

EOT failure = HCV RNA \geq LLOQ at end of treatment with at least 6 weeks of treatment, where the HCV RNA value must be collected on or after Study Drug Day 36 and study drug duration \geq 36 days.

On-treatment virologic failure = Breakthrough or EOT failure; if a subject meets both definitions of Breakthrough and EOT failure, he or she will be categorized as Breakthrough only.

SVR₄ = HCV RNA < LLOQ in the SVR₄ window (4 weeks after the last actual dose of study drug) without any confirmed quantifiable (\geq LLOQ) post-treatment value before or during that SVR window.

SVR₁₂ = HCV RNA < LLOQ in the SVR₁₂ window (12 weeks after the last actual dose of study drug) without any confirmed quantifiable (\geq LLOQ) post-treatment value before or during that SVR window.

SVR₂₄ = HCV RNA < LLOQ in the SVR₂₄ window (24 weeks after the last actual dose of study drug) without any confirmed quantifiable (\geq LLOQ) post-treatment value before or during that SVR window.

Relapse₁₂ = confirmed HCV RNA \geq LLOQ between end of treatment and 12 weeks after last actual dose of study drug (up to and including the SVR₁₂ window) for a subject with HCV RNA < LLOQ at Final Treatment Visit who completed treatment, excluding reinfection as described below.

Relapse₂₄ = confirmed HCV RNA \geq LLOQ within the SVR₂₄ window for a subject who achieved SVR₁₂ and has HCV RNA data available in the SVR₂₄ window, excluding reinfection.

Relapse_{overall} = confirmed HCV RNA \geq LLOQ between end of treatment and up to and including the last HCV RNA measurement collected in the Post-Treatment Period for a subject with HCV RNA < LLOQ at Final Treatment Visit who completed treatment, excluding reinfection.

Virologic failure = On-treatment virologic failure or Relapse_{overall}

Only subjects who have at least one post-treatment HCV RNA value will be included in analyses of relapse. For the analysis of relapse, completion of treatment is defined as any subject with study drug duration of 77 days or greater for Arm A and 103 days or greater for Arm B. If the last available post-treatment value is \geq LLOQ, then the subject will be considered a relapse (i.e., will not require confirmation).

HCV reinfection is defined as confirmed HCV RNA \geq LLOQ after the end of treatment in a subject who had HCV RNA $<$ LLOQ at Final Treatment Visit, along with the post-treatment detection of a different HCV genotype, subtype, or clade compared with baseline, as determined by phylogenetic analysis of the NS3/4A, and/or NS5A, and/or NS5B gene sequences. Reinfection in the case of the same HCV subtype is defined as a clade switch, as indicated by the lack of clustering between the baseline and post-treatment sequences by phylogenetic analysis. If phylogenetic analysis is not possible due to technical difficulties, HCV reinfection may be determined with a confirmed HCV genotype or subgenotype switch by the Versant HCV Genotype Inno-LiPA Assay v2.0 or Sanger assay.

Post-treatment relapse is defined as described earlier (**Relapse₁₂**, **Relapse₂₄**, **Relapse_{overall}**), and no genotype, subtype, or clade switch compared with baseline as determined by phylogenetic analysis of the NS3/4A, and/or NS5A, and/or NS5B gene sequences. If phylogenetic analysis is not possible due to technical difficulties, the subject will be defined as having a post-treatment relapse unless an HCV genotype or subgenotype switch is confirmed by the Versant HCV Genotype Inno-LiPA Assay v2.0 or Sanger assay.

Reasons for SVR₁₂ Non-Response

Subjects who do not achieve SVR₁₂ (SVR₁₂ non-responders) will be categorized as having:

1. On-treatment virologic failure;
2. HCV reinfection;

3. Relapse₁₂;
4. Prematurely discontinued study drug with no on-treatment virologic failure (defined as any SVR₁₂ non-responder who prematurely discontinued study drug [study drug duration < 77 days for Arm A, or < 103 days for Arm B] and did not meet the **On-treatment virologic failure or HCV reinfection** definitions);
5. Missing follow-up data in the SVR₁₂ window (defined as any subject who completed study drug without data in the SVR₁₂ window after applying the imputation rules and not meeting the definitions of [1], [2], [3], or [4]);
6. Other (defined as any SVR₁₂ non-responder not meeting the definitions of [1] – [5]).

Reasons for SVR₂₄ Non-Response

Subjects who do not achieve SVR₂₄ (SVR₂₄ non-responders) will be categorized as having:

1. On-treatment virologic failure;
2. HCV reinfection;
3. Relapse₁₂;
4. Relapse₂₄;
5. Prematurely discontinued study drug with no on-treatment virologic failure (defined as any SVR₂₄ non-responder who prematurely discontinued study drug [study drug duration < 77 days for Arm A, or < 103 days for Arm B] and did not meet the **On-treatment virologic failure, HCV reinfection, Relapse₁₂, or Relapse₂₄** definitions);
6. Missing follow-up data in the SVR₂₄ window (defined as any subject who completed study drug without data in the SVR₂₄ window after applying the imputation rules and not meeting the definitions of [1], [2], [3], [4], or [5]);

7. Other (defined as any SVR₂₄ non-responder not meeting the definitions of [1] – [6]).

For the reasons for SVR₁₂ and SVR₂₄ nonresponse defined above, subjects are only to be counted in one category in the order shown above.

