10.4 Secondary Efficacy Analyses

The secondary efficacy endpoints are:

- The percentage of subjects with on-treatment virologic failure;
- The percentage of subjects with Relapse₁₂.

The number and percentage of subjects with on-treatment virologic failure and Relapse₁₂ in the ITT population will be summarized along with two-sided 95% Wilson score CIs.

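### An isolated quantifiable HCV RNA value at the final treatment visit makes a subject an on-treatment virologic failure even when the same subject achieves SVR12

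*SAP*

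**What the plan says.** All of the following is in SAP 10.1 unless another section is named.

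- **EOT failure** is HCV RNA ≥ "LLOQ at end of treatment with at least 6 weeks of treatment". Two timing conditions apply: the sample is taken no earlier than day 36, and dosing has lasted at least 36 days. No second sample is asked for. The detection and quantification limits "for this assay (regardless of genotype) are both 15 IU/mL".
- **Confirmation on treatment.** The rule asks for two successive values at or above the LLOQ, with 100 IU/mL replacing the LLOQ for Breakthrough. The pair may fall "either both during treatment or at the final treatment measurement and the next consecutive post-treatment measurement".
- **OTVF** is "Breakthrough or EOT failure; if a subject meets both definitions of Breakthrough and EOT failure, he or she will be categorized as Breakthrough only".
- **SVR12** is "HCV RNA < LLOQ in the SVR₁₂ window (12 weeks after the last actual dose of study drug"), provided there is no confirmed quantifiable post-treatment value up to and including that window. Both values of such a confirmed pair must be post-treatment.
- **Secondary endpoint (SAP 10.4).** "The percentage of subjects with on-treatment virologic failure" is reported for the ITT population with a Wilson interval.
- **Reasons for non-response.** OTVF is the first category, but the table covers SVR12 non-responders only.
- **Additional endpoint (SAP 10.7).** Virologic failure through Post-Treatment Week 24 is limited to SVR24 non-responders.

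Protocol 5.4.1.1 gives two OTVF criteria for subject management. Both need confirmation, and neither is an EOT failure. SAP 12.1 does not list EOT failure among its changes from the protocol.

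**The concern.** The SAP sets up a confirmation rule at the LLOQ for on-treatment values and then never uses it. Breakthrough has its own 100 IU/mL threshold and its own log-increase rule. SVR and relapse use the post-treatment rule. EOT failure is the one endpoint the LLOQ rule would fit, and its definition omits the word.

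The result is uneven. After suppression, a single mid-treatment value of 100 IU/mL that is < LLOQ on the next sample is not a Breakthrough under the 100 IU/mL criterion. A single value of 15 IU/mL at the final visit is an OTVF, whatever follows.

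OTVF is one of only two secondary efficacy endpoints. As written it can count subjects whom the primary endpoint counts as responders. The OTVF count under SAP 10.4 can then exceed the OTVF count in the non-response table, and a reader of the report would have no rule to reconcile them.

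**Working it through.** **Inputs.** LLOQ 15 IU/mL (SAP 10.1). Planned N is 5 in Arm A, 45 in Arm B and 50 overall (SAP 4.2). Intervals are two-sided 95% (protocol 8.1), so z = 1.960.

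**Step 1: reproduce the plan's own figures.** The Wilson interval is

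[p + z²/(2n) ± z·√(p(1−p)/n + z²/(4n²))] / (1 + z²/n).

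For one failure in 50, p = 0.98. The centre is (0.98 + 0.0384)/1.0768 = 0.9457 and the half-width is 1.960 × 0.02786/1.0768 = 0.0507. This gives 89.5% to 99.6%, as in SAP Table 3. All 15 intervals in that table reproduce to 0.1 point, and none is in dispute.

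**Step 2: apply the definitions to every pattern.** Take the value before the final treatment visit, the final treatment value (EOT), PT Week 4 and PT Week 12, each < LLOQ (−) or ≥ LLOQ (+). Assume + values of 15 to 99 IU/mL, no Breakthrough, a completed course and one sample per window. There are 16 patterns. The 8 with EOT < LLOQ cannot be EOT failures. The other 8 are:

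| Before EOT | EOT | PT 4 | PT 12 | SVR12 | OTVF as written | OTVF if confirmation were the only change | OTVF under the fix to 10.1 |
|---|---|---|---|---|---|---|---|
| − | + | − | − | yes | yes | no | no |
| − | + | − | + | no | yes | no | yes |
| − | + | + | − | yes | yes | yes | yes |
| − | + | + | + | no | yes | yes | yes |
| + | + | − | − | yes | yes | yes | yes |
| + | + | − | + | no | yes | yes | yes |
| + | + | + | − | yes | yes | yes | yes |
| + | + | + | + | no | yes | yes | yes |

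As written, 4 of the 16 patterns are both SVR12 and OTVF: every pattern with EOT ≥ LLOQ and PT Week 12 < LLOQ. Row 1 is the isolated value, for example EOT 20 IU/mL and < 15 IU/mL afterwards. Requiring confirmation under the SAP's full rule removes row 1 and leaves 3 overlaps. In rows 3 and 7 the lone positive post-treatment value is not a confirmed pair, so SVR12 stands. In row 5 both confirming values are on treatment, where SVR12 does not look.

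**Step 3: what confirmation alone would break.** Row 2 is a rebound after an unconfirmed EOT value. Relapse12, Relapse_overall and reinfection all require HCV RNA < LLOQ at the Final Treatment Visit. With confirmation alone, this subject would be neither OTVF nor relapse, would fall to category 6 (Other) in the reasons table, and would leave mITT-VF as a supposed non-virologic non-responder.

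**Step 4: size.** The same formula with x failures in n:

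| | 0 subjects | 1 subject |
|---|---|---|
| Overall, n = 50 | 0% (0.0% to 7.1%) | 2.0% (0.4% to 10.5%) |
| Arm B, n = 45 | 0% (0.0% to 7.9%) | 2.2% (0.4% to 11.6%) |
| Arm A, n = 5 | 0% (0.0% to 43.4%) | 20.0% (3.6% to 62.4%) |

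SVR12 is the same in both columns. The documents do not say how often this happens. If 0 to 2 subjects are assumed, the overall effect is 0 to 4 points (2/50 = 4.0%, 1.1% to 13.5%).

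**The case against.** The strongest reply is that the single-value rule has a purpose. For treatment completers, EOT ≥ LLOQ and the < LLOQ condition at the Final Treatment Visit are complements, so a virologic failure falls on one side or the other. Adding confirmation without a safeguard opens the gap in step 3, and that misclassification would favour the regimen, whereas the present double count works against it. This stands, and it shapes the fix.

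The reply is also right that missing confirmation is not the whole cause. SVR12 takes no account of on-treatment results, so even a confirmed Breakthrough who later clears would be both OTVF and SVR12.

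A reader might infer three stronger things that the documents do not support:

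- **That the primary result is distorted.** It is not. SVR12 does not use the EOT value, and mITT-VF removes only non-responders, so a responder stays in it.
- **That the reported outcomes must add to more than 100%.** The SAP never adds SVR12, OTVF and relapse. Its reasons table is confined to non-responders, with one category each, and is consistent in itself.
- **That the protocol is contradicted.** The criteria in protocol 5.4.1.1 are stated for subject management, so an extra analysis category in the SAP is not a contradiction in itself, although SAP 12.1 does not mention it.

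The unused LLOQ rule suggests that the authors meant it for EOT failure, but the text does not say so. That does not remove the problem: even if a single value was intended, the SAP gives no rule for a subject who is both OTVF and SVR12.

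**Conclusion.** The point holds as a gap in definition. On the text as written, a subject with an isolated final-visit value of 15 IU/mL or more is counted as both cured and failed, and SAP 10.4 and the non-response table can report different OTVF counts. SAP 10.7 avoids this for its own endpoint; 10.4 does not.

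The effect is confined to a descriptive secondary endpoint in a study with no hypothesis test. It is 2.0 points overall per subject, 2.2 in Arm B and 20 in Arm A, the last being large only because N is 5. These figures rest on the planned arm sizes and illustrate one subject; the frequency is unknown and may be zero. The change is worth making because it costs little and the present rule can label responders as failures.

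**What to change.** **SAP 10.1.** Count an EOT value ≥ LLOQ, with the existing Day 36 and duration conditions, as EOT failure if any of these holds:

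1. it is confirmed under the SAP's full on-treatment rule (two consecutive values ≥ LLOQ, both on treatment, or the final treatment value and the next post-treatment value);
2. no later HCV RNA value exists;
3. the subject is an SVR12 non-responder.

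Condition 3 keeps a rebound such as row 2 as a virologic failure and inside mITT-VF. Condition 2 is normally covered by condition 3, because missing data count as failure, but it mirrors the exception already given for Breakthrough.

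**SAP 10.4.** State how a subject who still meets both OTVF and SVR12 is counted. One option is to report OTVF among SVR12 non-responders, parallel to the restriction in 10.7. That brings the remaining overlaps to zero and makes the count agree with the reasons table. List the subjects concerned either way, and record the change in SAP 12.1.

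**Cost.** The definition becomes slightly more complex, there is a small programming change, and the OTVF rate may be slightly lower than under the single-value rule. One rare case needs a decision. A subject with an unconfirmed EOT value, SVR12 and a confirmed rebound in the SVR24 window would be Relapse24 but not Relapse_overall, and so would drop out of the 10.7 virologic failure count unless condition 3 is extended to SVR24 non-responders for that endpoint.

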8.1.2.2 Secondary Efficacy Endpoints

The secondary efficacy endpoints are:

- The percentage of subjects with HCV on treatment virologic failure by treatment arm and overall;
- The percentage of subjects with post-treatment HCV virologic relapse by treatment arm and overall. Subjects with reinfection will be summarized separately.

For the analysis of HCV virologic relapse, completion of treatment is defined as any subject with study drug duration of 77 days and 103 days or greater for subjects allocated to treatment durations of 12 weeks and 16 weeks, respectively.

For each treatment arm and overall, as applicable, the number and percentage of subjects meeting each secondary efficacy endpoint will be summarized along with a two-sided 95% confidence interval using Wilson's score method.

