4.2 Design Diagram

Study M15-942 is a Phase 3b, open-label, non-randomized, multicenter study to evaluate the efficacy and safety of ABT-493/ABT-530 in combination with SOF and RBV in HCV GT1 – 6 infected subjects, including subjects with compensated cirrhosis and/or HIV-1 co-infection and/or post-liver or post-renal transplant, who have experienced virologic failure while participating in an AbbVie HCV parent study.

It is anticipated that approximately 50 HCV-infected subjects who have experienced virologic failure following treatment with regimens containing ABT-493/ABT-530, 3D or 2D in one of the AbbVie HCV parent studies will be enrolled. Subjects will be allocated to the 12-week treatment duration (Arm A) or the 16-week treatment duration (Arm B) based on HCV GT, cirrhosis status, and treatment experience with PI and/or NS5Ai-containing regimens prior to enrolling in the AbbVie HCV parent studies, as defined in [Table 1](#).

Table 1. Treatment Arm Allocation in Study M15-942

Patient Population			
Genotype**	Cirrhotic Status*	PI and/or NS5Ai-Experienced Prior to the AbbVie HCV Parent Study	Study M15-942 Treatment Arm
1, 2, 4, 5 and/or 6	NC	No	A
3	Any	Any	B
Any	C	Any	B
Any	Any	Yes	B

* NC = non-cirrhotic; C = cirrhotic

** If the subject's HCV GT at Screening is unknown, or if it is mixed and includes GT3, then the subject will be assigned to Arm B (16 weeks), regardless of the cirrhosis status or PI and/or NS5Ai use prior to the AbbVie HCV Parent Study.

Arm A will enroll approximately 5 subjects, and Arm B will enroll approximately 45 subjects. Subjects will receive ABT-493/ABT-530 300 mg/120 mg QD, SOF 400 mg QD, and RBV 600 to 1200 mg daily in two divided doses, orally, for 12 (Arm A) or 16 (Arm B) weeks (Figure 1). Dosing of RBV will be based on baseline age and weight as defined in Table 2.

Scheduled visits for subjects in the Treatment Period consist of Day 1 and Weeks 2, 4, 8, and 12 for all subjects and an additional Week 16 visit for subjects in Arm B. Subjects who complete or prematurely discontinue study drug will be followed for 24 weeks. During the Post-Treatment Period, all subjects will have visits at Post-Treatment Weeks 4, 12, and 24.

Figure 1. Study Schematic

[figure not shown]

Table 2. Ribavirin Dosing Recommendations

Age at Baseline (Years)	Body Weight at Baseline (kg)	Daily Dose (mg)	Number of 200 mg Tablets Per Period of the Day
≥ 18	< 75	1000	5 tablets
	≥ 75	1200	6 tablets
≥ 12 and < 18	35 – 46	600	3 tablets

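### SAP 10.1 waives confirmation of a last post-treatment value for relapse but not for reinfection, and its two relapse sentences conflict when a genotype switch is shown

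*SAP*

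**What the plan says.** All the rules are in SAP 10.1.

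- **Confirmation.** "A confirmed quantifiable post-treatment value is defined as any two consecutive post-treatment HCV RNA measurements" at or above LLOQ.
- **Waiver for relapse.** If the last available post-treatment value is at or above LLOQ, "then the subject will be considered a relapse (i.e., will not require confirmation". The sentence makes no exception for reinfection.
- **Completion.** Relapse applies to subjects who completed treatment, meaning "study drug duration of 77 days or greater for Arm A and 103 days or greater for Arm B".
- **Reinfection.** "HCV reinfection is defined as confirmed HCV RNA" at or above LLOQ after treatment, in a subject below LLOQ at the Final Treatment Visit, with a different genotype, subtype or clade detected. There is no last-value waiver.
- **No-switch condition.** A later paragraph takes the three relapse definitions and adds "and no genotype, subtype, or clade switch compared with baseline as determined by phylogenetic analysis".
- **Hierarchy.** For the non-response reasons, "subjects are only to be counted in one category in the order shown above". Reinfection ranks second, ahead of relapse.

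Protocol 5.4.1.1 requires confirmed HCV RNA for relapse and for reinfection alike, with no waiver for either. Protocol 8.1.2.2 adds: "Subjects with reinfection will be summarized separately". SAP 4.2 states that "all subjects will have visits at Post-Treatment Weeks 4, 12, and 24", so no draw is scheduled after Week 24.

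**The concern.** A subject whose only quantifiable post-treatment value is the last one, and whose virus is shown to differ from baseline, cannot reach the reinfection category under the rules as written. Two sentences in the same SAP section then give opposite answers on whether that subject is a relapse, so the label depends on which one is programmed.

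The label matters because the SAP's virologic failure includes relapse and not reinfection. Relapse12 is a secondary endpoint, and mITT-VF removes SVR12 non-responders whose reason is not virologic failure. The protocol also promises a separate account of reinfection, from which this subject would be missing. Settling the label once such a case has been seen would be post hoc.

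**Working it through.** No stated figure is in dispute. The check applies the SAP 10.1 rules in order to one record: below LLOQ at the Final Treatment Visit, a single last post-treatment value at or above LLOQ, and a switch shown.

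| Record | Waiver read literally | No-switch condition applied |
|---|---|---|
| Completer, value in the SVR12 window | Relapse12 (category 3) | *Other* (6) |
| Completer, last value before the SVR12 window | Relapse12 (3) | Missing follow-up data (5) |
| Premature discontinuer, SVR12 reasons | Premature discontinuation (4) | Premature discontinuation (4) |
| Completer with SVR12, value first seen at Post-Treatment Week 24 | Relapse24 and Relapse_overall | *Other* for SVR24 |

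No row gives reinfection. Two phrases that might seem to help do not:

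- The relapse definitions exclude reinfection, but this subject does not meet the reinfection definition, so the exclusion is not triggered.
- The LiPA/Sanger sentence also speaks of confirmation, but of the genotype switch, and only where phylogenetic analysis is not possible. It does not relax the RNA requirement.

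What each label can move:

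- **ITT SVR12:** nothing. The subject is a non-responder under every label, or already a responder if the value first appears at Week 24.
- **Value first seen at Week 24:** Relapse24, Relapse_overall, virologic failure through Post-Treatment Week 24 and the SVR24 reason table. The subject is an SVR12 success in mITT-VF and is not Relapse12.
- **Viremic by the SVR12 window, no later sample, filed as relapse:** Relapse12 and mITT-VF SVR12.
- **Filed as *Other* or missing follow-up data:** only the reason label. These categories and reinfection all lie outside virologic failure and are all excluded from mITT-VF.

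For scale in the third case, use the two-sided 95% Wilson interval, with p = x/n and z = 1.96:

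(p + z²/2n ± z·√[p(1−p)/n + z²/4n²]) / (1 + z²/n)

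This formula reproduces all 15 intervals in SAP Table 3 to the printed decimal. The inputs are the planned sizes, 45 in Arm B and 50 overall. The assumptions are one such subject (in Arm B), no other failure, and everyone counted in the relapse denominator.

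Worked example, x = 1, n = 45: p = 0.0222 and z²/n = 0.0854. The centre is (0.0222 + 0.0427)/1.0854 = 0.0598 and the half-width is 1.96 × 0.0309/1.0854 = 0.0559, giving 0.4% to 11.6%.

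| Measure | Filed as relapse | Filed as reinfection |
|---|---|---|
| Relapse12, Arm B | 1/45 = 2.2% (0.4, 11.6) | 0/45 = 0.0% (0.0, 7.9) |
| Relapse12, overall | 1/50 = 2.0% (0.4, 10.5) | 0/50 = 0.0% (0.0, 7.1) |
| mITT-VF SVR12, Arm B | 44/45 = 97.8% (88.4, 99.6) | 44/44 = 100% (92.0, 100.0) |
| mITT-VF SVR12, overall | 49/50 = 98.0% (89.5, 99.6) | 49/49 = 100% (92.7, 100.0) |
| ITT SVR12, Arm B | 44/45 = 97.8% (88.4, 99.6) | 44/45 = 97.8% (88.4, 99.6) |

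**The case against.** The best defence is that the SAP can be read as a whole. The no-switch condition comes after the waiver, is more specific, and is attached to all three relapse definitions. The waiver's parenthesis suggests that it relaxes only the two-value requirement. On that reading a proven switch is never relapse, and the shifts in Relapse12 and mITT-VF are zero. This is a reasonable reading and may be the intended one. But the waiver sentence is unconditional and nothing says which sentence governs. Even on this reading the subject falls into a residual category, not reinfection.

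A second defence is that asking for confirmation before granting reinfection is conservative, since that label takes the subject out of virologic failure, and that it follows Protocol 5.4.1.1. That is true of the protocol, but the protocol asks the same of relapse. The SAP dropped the requirement for relapse alone, and SAP 12.1 does not list the change.

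Third, the case is rare. It needs a reinfection seen only at the last sample, and the SAP's sequencing needs HCV RNA of at least 1000 IU/mL. The scheduled Week 24 visit would normally supply a second value for anyone viremic by Week 12. Non-responders are also listed individually with their reason, so a reader could spot the case. All of this stands, and it keeps the point small.

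**Conclusion.** The gap and the conflict are real, and their reach is narrow. For a completer with a proven switch at a single last value, SAP 10.1 gives relapse or a residual category depending on the sentence applied, and reinfection under neither. For the SVR12 reasons, premature discontinuers go to the discontinuation category.

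A reader might infer that the primary result is exposed, or that viremia first seen at Week 24 would lower mITT-VF SVR12. The documents support neither. ITT SVR12 does not depend on the label, and mITT-VF is defined by SVR12 status, which a Week 24 value does not alter. Nor is relapse the certain label, because the no-switch condition points the other way.

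The size is 2.2 points in Arm B or 2.0 points overall per subject on Relapse12, with a matching fall in mITT-VF SVR12. It arises only for a subject viremic by the SVR12 window, with no later sample, and filed as relapse. The documents give no count of such subjects; 0 or 1 of about 50 is an assumption. This is a minor clarification, worth making before the data are classified.

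**What to change.** 1. In the SAP 10.1 last-value sentence for relapse, add: *unless a switch of genotype, subtype or clade from baseline is shown*.
2. In the SAP 10.1 reinfection definition, keep the condition of HCV RNA below LLOQ at the Final Treatment Visit, and accept either confirmed HCV RNA at or above LLOQ or a last available post-treatment value at or above LLOQ, in each case together with the detected switch.
3. List both last-value waivers in SAP 12.1 as departures from Protocol 5.4.1.1, which requires confirmation for both outcomes.

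Every record in the first table then falls under reinfection. The cost is three short SAP edits, with no new data or visits. The downside is small: reinfection, which lies outside virologic failure, could be assigned on one RNA value, though only with sequence or genotype evidence of a different virus.
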